Desensitization to tDCS headband: Children with ASD may not tolerate wearing the tDCS headband for 20 minutes while engaged in ABA therapy. In order to facilitate tolerance and cooperation, we will provide 2-3 desensitization sessions per day during a week-long period. An eligible participant must be able to wear the headset for the full 20 minutes during the last two desensitization sessions in order to enroll in the study.

Removal of tDCS headband: Despite these desensitization efforts, in a population of children with ASD, it is possible that participants may remove the tDCS headband during stimulation. This has occurred during our preliminary work, especially at 1.5mA (note that we are proposing to use 1.0mA in this study). The tDCS device however can immediately sense the change in impedance and turn itself off automatically. We were able to reinstitute the treatment in a relatively short amount of time (<1 min) and the participant received the full length of treatment. It is unlikely that a short interruption would change the effects of the treatment.

Non-consecutive sessions: We are proposing to stimulate participants during their weekday ABA sessions. It is possible that for a portion of the participants, completing 5-consecutive tDCS sessions during their ABA therapy may not be possible due to participant and/or therapist absence (holidays, illness, etc.). In such cases, we will make up those missed stimulation sessions in order to administer the total number of active and sham tDCS.

Research Timeline -

Please note that the study participant will continue with ABA intervention throughout the entire study.

Enrollment

Week 1-

Daily Living Skills: Each participant will be given the Vineland Adaptive Behavior Scale (VABS-III). It assesses personal and social functioning for those up to 90 years of age, administered to a parent or caregiver using a semi-structured interview format. **The Medical History and Medication History will be obtained.**

Week2-4

Cognitive Profile: Results of cognitive testing (in IEP or psychological report provided by parent). A Leiter 3 cognitive assessment will be administered to study participant if the participant does not have a recent cognitive assessment (within past 3 years). ...

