1.5 Sample Size Justification

Protocol Version Date: V3 CLEAN 4 8 2021

This is a pilot study. Long-term objective for this proposal will be to accumulate treatment outcome data, EEG biomarker data and safety evidence, to warrant an adequately powered clinical trial

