4.0 Subject Considerations

4.1 Subject Selection and Enrollment Considerations

1. Method to Identify Potential Subjects: Participants will be recruited from the local New Jersey ABA providers or healthcare providers in New Jersey. New Jersey has one of the highest rates of autism in the United States. Based on the gender distribution of ASD in the population, we expect that our group will be approximately 75% male) but will include subjects from ethnic groups representative of NJ counties. We do not anticipate challenges related to recruitment.

2. Recruitment Details:

- a. Identify Potential Subjects- We will begin with a kickoff meeting with local ABA providers to discuss the study with the PI Co-Investigators and study coordinator. The meeting will be virtual using WebEx. We will also publish an informational study flyer with general study details and contact information for the study coordinator. The flyer will be distributed to ABA providers or used to publish on RWJ research website, Autism New Jersey, Autism Speaks, ABA provider websites or on other autism websites.
 - A phone line will be set up for families or ABA providers to discuss the study as well as for participants to learn more about the study and set up a telephone screening intake if interested.
 - The Research Coordinator /Research Assistants- will complete a telephone Screening (determine eligibility by inclusion and exclusion criteria). Eligible families considering participation can ask specific questions and discuss specific study details with the research assistant or PI. Information regarding the study will be emailed to participant families to review (consent forms).

3. Inclusion Criteria

- 1. Males and females between 5 and 12 years with autism
- 2. Enrolled in a New Jersey ABA-based program (school or in-home) supervised by a Board-Certified Behavior Analyst (BCBA)
- 3. Stable medical and behavioral treatments for at least 4 weeks prior to, and during the study

4. Able to tolerate wearing tDCS as determined during a week-long daily desensitization training.

4. Exclusion Criteria

- 1. Any implanted metal device (heart pacemaker, cochlear implant, surgical clips, etc.)
- 2. Severe neurological disorders such as TBI, brain tumor, intracranial infection
- 3. Seizure disorder with a seizure within the last two years
- 4. Skull defect
- 5. Peripheral blindness or deafness

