4.6 Economic Burden and/or Compensation for Subjects

A. Expenses

There will be no cost to the participant and his/her family for participating in this study. Parking costs will be reimbursed for study visits that require the participant and/or his/her legally acceptable representatives to be present at RWJMS,

- B. Compensation/Incentives- N/A
- C. Compensation Documentation N/A
- 4.7 Risks of Harm/Potential for Benefits to Subjects
 - A. Description of Risks of Harm to Subjects-Reasonably Foreseeable Risks of Harm

The safety of tDCS is remarkable, compared to nearly any other biologic treatments which have been used. In a review of over 30,000 treatment episodes, there were no serious side effect noted (Bikson, Grossman et al., 2016). Safety in children has also been addressed and is comparable to adults, The most common side effect is a tingling feeling under the electrode (which is short lived) in about 10% of children. Over time children will get used to the tingling. About 5% of children report some temporary itching or reddening under the electrode (Krishnan, Santos et al., 2015). The redness should dissipate within five minutes. Parents and therapists will be instructed to look for any rashes to keep the child from touching or picking at the area.

B. Risk of Harm from an Intervention on a Subject with an Existing Condition

tDCS is a considered a safe and tolerable procedure. This research presents the prospect of direct benefit to the individual participant, and there is evidence that tDCS improves learning and improves the core symptoms of ASD as well as co-morbidities. The risk to participants is minimal compared to benefits. In addition, participants will be monitored throughout the study for tolerability, any side effects, or changes in health.

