 - A member of the study team will observe the placement and removal of the tDCS device for each ABA session via video conferencing. The treatment will be discontinued when the child participant is crying (more than 5 min), is pulling at the device or equipment, or asking to stop, or if not participating in therapy. Information will be recorded on the treatment log.
- Parents and therapists will be instructed to monitor for redness under the electrode site and to keep the child from touching the area (i.e., cover with band aid). Any redness persisting greater than 2 hour or if there are any signs of skin abrasion/ lesion will be considered an adverse event reportable to the IRB.
- > tDCS will be suspended during illness such as viral illness with fever, if there are skin irritation requiring medical treatment or if the child is being evaluated for new neurological or medical conditions i.e., seizures / diabetes.
- Subjects may become be discharged from the study if there are changes in their medical history/ /medication treatment (ex. a new medication is prescribed that makes the participant ineligible). Following this training, the parent will be able to conduct the entire tDCS procedure independently. In certain cases that require additional assistance, a study staff will be available through the telemedicine portal to assist the parent during the sessions. We do not anticipate that many parents will require more than 1-2 training sessions

6.3bData/Safety Monitoring Board Details N/A

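### The pilot is meant to accumulate safety evidence, but it plans no side-effect or tolerability measure, and its one specific adverse-event rule misses the effects the protocol expects

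*Combined protocol and SAP*

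**What the plan says.** **Aim.** Section 1.5 says the longer-term purpose is to "accumulate treatment outcome data, EEG biomarker data and safety evidence" that would justify a larger trial. Section 1.6 B repeats this under Aim 2.

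**Expected effects.** Section 4.7 A: "The most common side effect is a tingling feeling under the electrode (which is short lived) in about 10% of children". Also: "About 5% of children report some temporary itching or reddening under the electrode". On duration: "The redness should dissipate within five minutes".

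**Adverse-event rule.** Section 6.3a: "Any redness persisting greater than 2 hour or if there are any signs of skin abrasion/ lesion will be considered an adverse event". The rest of that sentence makes such events reportable to the IRB. The same section requires prompt IRB reporting of adverse events in general, without defining the term further.

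**Monitoring.** Section 4.4 A provides daily contact during both stimulation phases. Section 4.7 B promises monitoring for tolerability and side effects, and a skin examination before and after each session. In 4.7 H and 6.3a, staff observe placement and removal of the device at each session. A treatment log is mentioned in 6.3a directly after the rule on discontinuing treatment, and its contents are not described. Section 6.3b lists no monitoring board.

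**Selection for tolerance.** Section 1.3: "An eligible participant must be able to wear the headset for the full 20 minutes during the last two desensitization sessions". Inclusion criterion 4 in section 4.1 reads: "Able to tolerate wearing tDCS as determined during a week-long daily desensitization training". Section 4.7 B removes children when tolerability is a concern. Section 1.3 replaces dropouts, giving each replacement a new study ID.

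**The concern.** Section 1.5 names three kinds of evidence, and only two of them have a measure, a visit schedule and an analysis. The third, safety, has a general promise of monitoring and one threshold that lies beyond everything the protocol expects to see. A pilot run to the letter could report few or no adverse events while saying little about tingling, itching or ordinary redness, and could have no planned comparison of active with sham.

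That comparison matters because section 1.3 says sham also produces the initial tingling, so a pooled rate cannot be attributed to active current. Mild sensations not asked about at the session cannot be recovered afterwards.

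The tolerability figure raises a second, separate issue. If it is reported among completers, it describes children who passed a headset test and were not later removed. The next trial could then be planned on a retention rate that does not apply to the children it approaches.

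**Working it through.** The plan gives no safety sample size or detectable rate, so there is no stated figure to reproduce.

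**1. The three kinds of evidence side by side**
- Treatment outcome: BRIEF, PDDBI and discrete-trial data in 1.6 B; weeks 4, 8, 12, 16 and 20 in Table 2; tests of the BRIEF and PDDBI in 6.1.
- EEG biomarker: Aim 2 in 1.6 B; the same five weeks in Table 2; its own part of 6.1.
- Safety: no variable in 1.6 B, no row in Table 2 (or its repeat in 1.10), no analysis in 6.1.

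**2. The rule against the expected effects**
- Redness: threshold 2 h = 120 min, expected duration 5 min; 120 / 5 = 24. The threshold is 24 times the expected duration.
- Tingling and itching: not mentioned in the rule.
- Abrasion or lesion: counted without a time limit, so the rule is not empty. Section 4.7 B notes that some children may pick at their skin. These are not the effects that 4.7 A quantifies.

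**3. Expected number of affected children**

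Inputs: 10% and 5% from 4.7 A; n = 24 enrolled and n = 20 completing from 4.3. Expected count = n × p. P(at least one) = 1 − (1 − p)^n, assuming children are independent.
- Tingling, n = 24: 24 × 0.10 = 2.4; 1 − 0.90^24 = 0.920.
- Tingling, n = 20: 20 × 0.10 = 2.0; 1 − 0.90^20 = 0.878.
- Itching or reddening, n = 24: 24 × 0.05 = 1.2; 1 − 0.95^24 = 0.708.
- Itching or reddening, n = 20: 20 × 0.05 = 1.0; 1 − 0.95^20 = 0.642.

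The pilot is therefore likely to contain at least one child with each effect. As 4.7 A describes them, none of these effects meets the 6.3a rule.

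**4. What zero qualifying events would show**

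The one-sided 95% upper bound for zero events is 1 − 0.05^(1/n).
- n = 24: 11.7%.
- n = 20: 13.9%.

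Even for the events the rule does count, a clean record would leave a wide range of true rates open.

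**5. What systematic recording would give**

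Exact two-sided 95% intervals near the expected counts:
- 2 of 24 children: 1.0% to 27.0%.
- 1 of 24 children: 0.1% to 21.1%.

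These are wide. A table by condition would be descriptive and would not be a test.

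**6. Denominators for tolerability**
- Completers: all tolerated the procedure, by selection.
- Enrolled: between 20/24 = 83% (if all four planned losses were for tolerance) and 24/24 = 100% (if none were). The documents do not give the share.
- Starting desensitization: the documents give no number, so the effect of the run-in cannot be sized.

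**The case against.** The strongest reply is that the plan already watches for side effects. It has daily contact, a skin examination around each session, staff observation, a log and a general duty to report adverse events. The 2-hour rule is tied to IRB reporting and need not limit what is written down. The log and the procedure manual mentioned in 2.2 are not among the documents, and the available text is incomplete after the endpoints item in 1.3, so the recording may be better specified elsewhere. Safety evidence is also worded as a long-term objective and is in neither Aim 1 nor Aim 2.

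Much of this stands, and it rules out several stronger readings that a reader might infer:
- *Expected effects will go uncounted.* Not supported. Some may well be observed and logged. What is missing is a defined way to record and tally them.
- *Active and sham cannot be compared.* Not supported. Treatment order is known and the phases have fixed weeks, so log entries can be assigned to a condition after unblinding. The comparison is unplanned.
- *The run-in removes the side effects.* Not supported. It tests wearing the headset, and no current is mentioned during desensitization. It selects on headset tolerance, which does not by itself remove current-related skin effects.
- *Planned completers divided by planned screens gives a tolerability rate.* Not supported. Section 4.1 describes telephone screening against a long list of exclusions, so some screened children may never try the headset.
- *Intolerant children vanish from the count.* Not supported. Replacements receive new IDs, so removed children remain identifiable, and nothing says that only completers will be reported.

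The reply does not supply a safety outcome, a list of solicited effects or a planned table by condition. If the 2-hour rule is only a reporting threshold, the documents contain no rule for collecting the milder effects at all.

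**Conclusion.** The concern holds in limited form. Safety evidence is something the pilot is to accumulate, but no safety or tolerability measure is defined, scheduled or analysed. The one specific adverse-event rule does not capture the effects the protocol expects: about 2.4 of 24 children with tingling and 1.2 of 24 with itching or reddening. These counts rest on the protocol's own literature rates, taken as given and applied per child. The tolerability point is separate: a rate among completers would describe a group selected for wearing the headset, by an amount the documents do not allow us to size.

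This should be changed before enrolment, because unsolicited mild effects cannot be reconstructed later. It does not affect the efficacy analysis. It would shrink to a matter of reporting if the log or manual already lists these effects for every session.

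**What to change.** 1. Add a short fixed checklist to the existing treatment log: tingling, itching, redness of any duration, headache, behaviour change, headset removal, session stopped early. Blinded study staff complete it at the observed removal of the device at every session.
2. In 6.1, plan a table of children with each effect by active and sham, with exact intervals, as description only.
3. Report the numbers failing desensitization and removed for tolerability, with all children who start desensitization as the denominator.
4. List side effects and tolerability as pilot outcomes in 1.6 B and add them to Table 2.

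The IRB reporting rule and the care rules stay as they are.

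**Cost.** About a minute per session at sessions staff already observe, plus one table. The reported tolerability rate may be less favourable. Staff are committed to observing only placement and removal, and 6.3a notes communication and sensory challenges in these children, so self-report of sensations will be limited. Asking about tingling or redness may also draw parents' attention to cues about the condition, and parents rate the primary outcome. Completion by blinded staff limits that risk but does not remove it.

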6.4 Reporting Results

A. Individual Subjects' Results N/A

B. Aggregate Results

Findings from the study such as abstracts or papers/presentations can be shared with all participants who express an interest in receiving a summary.

C. Professional Reporting

Preliminary research analysis and project related progress will be shared with the New Jersey Governor's Council for Medical Research and Treatment of Autism in quarterly and annual reports and research meetings. We will disseminate our research findings at professional meetings and publications in discipline-related journals.

D. Clinical Trials Registration, Results Reporting and Consent Posting The study will be registered at www.clinicaltrials.gov.

Protocol Title: A Pilot Study of Transcranial Direct Current Stimulation in Children with ASD

6.5 Secondary Use of the Data N/A

7.0 Research Repositories - Specimens and/or Data N/A

8.0 Approvals/Authorizations

Letters of Cooperation with Institute for Basic Research as well as Boston Children's Hospital.

Pro2020000931

